Template 33 Listing of adverse events, SAEs and solicited symptoms leading to withdrawal from the study <within 30 days (Days 1-30) post-vaccination period><during vaccination up to <Day 91, study end> <Exposed Set>

Group	Subject No.	Country	Race	AE Description	SAE	Causality	Outcome	Type of discontinuation

RSV MAT 30 = Subject receiving RSVPreF3 low dose

RSV MAT 60 = Subject receiving RSVPreF3 mid dose

RSV MAT 120 = Subject receiving RSVPreF3 high dose

Placebo = Subject receiving placebo

Please note that this table will be presented on group blinded during Day 91 analysis.

CONFIDENTIAL

208068 (RSV-MAT-001)
Statistical Analysis Plan Final

Template 34 Listing of all pregnancies from vaccination up to study end <Exposed Set>

Group No.	Sub.	Country	Race	Age at vaccination	LMP date	Age at pregnancy (Year)	Date of delivery	Pregnancy Outcome	Date of outcome	Gestational weeks at birth/miscarriage /termination

RSV MAT 30 = Subject receiving RSV PreF3 low dose

RSV MAT 60 = Subject receiving RSV PreF3 mid dose

RSV MAT 120 = Subject receiving RSV PreF3 high dose

Placebo = Subject receiving placebo

Template 35 Number and percentage of subjects with <RSV-A neutralising antibody titre, RSV IgG antibody concentration> equal to or above <cut-off> and <GMTs/GMCs> <PPS for immunogenicity, Exposed Set>

			≥cut-off unit			GMT/GMC						
			95% CI		95% CI							
Antibody	Group	Timing	N	n	%	LL	UL	value	LL	UL	Min	Max
<RSV-A NAb, RSV IgG antibody>	<each group>	PRE										
		PI(D8)										
		PI(D31)										
		PI(D61)										
		PI(D91)										

<each group>:

RSV MAT 30 = Subject receiving RSVPreF3 low dose

RSV MAT 60 = Subject receiving RSVPreF3 mid dose

RSV MAT 120 = Subject receiving RSVPreF3 high dose

Placebo = Subject receiving placebo

GMT/GMC = geometric mean antibody titre/concentration calculated on all subjects

N = Number of subjects with available results

n/% = number/percentage of subjects with titre equal to or above specified value

95% CI = 95% confidence interval; LL = lower limit, UL = upper limit

MIN/MAX = Minimum/Maximum

PRE= Pre-vaccination at screening

PI(D8) = Post-vaccination at Day 8

PI(D31) = Post-vaccination at Day 31

PI(D61) = Post-vaccination at Day 61

PI(D91) = Post-vaccination at Day 91

To check for the disclosure name for the antibody for 1st column of the table

Template 36 Distribution of RSV-A neutralising antibody titre <PPS for immunogenicity <at Day X>>

Antibody	Timing	Titre	Each group		
			N	n	%
RSV-A NAb	<PRE, PI(D8), PI(D31), PI(D61), PI(D91)>	<128			
		≥128			
		≥256			
		≥512			
		≥1024			
		≥2048			
		≥4098			

<each group>:

RSV MAT 30 = Subject receiving RSVPreF3 low dose

RSV MAT 60 = Subject receiving RSVPreF3 mid dose

RSV MAT 120 = Subject receiving RSVPreF3 high dose

Placebo = Subject receiving placebo

N = number of subjects with available results

n/% = number/percentage of subjects with titre within the specified criterion

PRE= Pre-vaccination at screening

PI(D8) = Post-vaccination at Day 8

PI(D31) = Post-vaccination at Day 31

PI(D61) = Post-vaccination at Day 61

PI(D91) = Post-vaccination at Day 91

Please note that the categories of the titre presentation are not fixed and will be adjusted at time of D91 analysis

Template 37 Distribution of fold of anti-RSV-A neutralising antibody titre by pre-vaccination titre category <PPS for immunogenicity>

Antibody	Fold change	Pre-vaccination status	Timing	Each group		
				N	n	%
RSV-A NAb	<1	<128	PI(D8)			
			PI(D31)			
			PI(D61)			
			≥128-≤256			
			≥256-≤512			
			≥512-≤1024			
			≥1024-≤2048			
		>2048-≤4096	≥2048-≤4096			
			>4096			
			Total			
		≥1 - <2				

<each group>:

RSV MAT 30 = Subject receiving RSVPreF3 low dose

RSV MAT 60 = Subject receiving RSVPreF3 mid dose

RSV MAT 120 = Subject receiving RSVPreF3 high dose

Placebo = Subject receiving placebo

N = number of subjects with pre- and corresponding post-vaccination results available

n/% = number/percentage of subjects with titre fold change meeting the specified criterion

PI(D8) = Post-vaccination at Day 8

PI(D31) = Post-vaccination at Day 31

PI(D61) = Post-vaccination at Day 61

PI(D91) = Post-vaccination at Day 91

Please note that the categories of the titre presentation are not fixed and will be adjusted at time of D91 analysis

Template 38 Geometric mean of the individual ratio of <RSV-A neutralizing antibody titres, RSV IgG antibody concentrations> at <Day 8, Day 31, Day 61, Day 91> compared to pre-vaccination with 95% CI <PPS for immunogenicity<at Day 31>>

Group	N	Time point description	<GMC,T>	Time point description	<GMT,C>	<GMT,C> ratio			95% CI	
						Ratio order	Value	LL	UL	
RSV MAT 30	PI(D31)		PRE		PI(D31) / PRE					
RSV MAT 60	PI(D31)		PRE		PI(D31) / PRE					
RSV MAT 120	PI(D31)		PRE		PI(D31) / PRE					
Placebo	PI(D31)		PRE		PI(D31) / PRE					

RSV MAT 30 = Subject receiving RSVPreF3 low dose

RSV MAT 60 = Subject receiving RSVPreF3 mid dose

RSV MAT 120 = Subject receiving RSVPreF3 high dose

Placebo = Subject receiving placebo

<GMT,C> = geometric mean antibody <titres, concentration> calculated on all subjects

N = Number of subjects with available results at the two considered time points

95% CI = 95% confidence interval; LL = lower limit, UL = upper limit

PRE= Pre-vaccination at screening

PI(D8) = Post-vaccination at Day 8

PI(D31) = Post-vaccination at Day 31

PI(D61) = Post-vaccination at Day 61

PI(D91) = Post-vaccination at Day 91

Template 39 Estimated <GMTs, GMCs> and 95% CIs for <RSV-A neutralising antibody titre, RSV IgG antibody concentration> (PPS for immunogenicity)

Antibody	Group	Timing	N	Estimated GMT		
				Value	LL	UL
<RSV-A NAb, RSV IgG antibody concentration>	RSV MAT 30	PRE				
		PI(D8)				
		PI(D31)				
		PI(D61)				
		PI(D91)				
	RSV MAT 60	PRE				
		PI(D8)				
		PI(D31)				
		PI(D61)				
		PI(D91)				
	RSV MAT 120	PRE				
		PI(D8)				
	Placebo	PRE				
		PI(D8)				

RSV MAT 30 = Subject receiving RSVPreF3 low dose

RSV MAT 60 = Subject receiving RSVPreF3 mid dose

RSV MAT 120 = Subject receiving RSVPreF3 high dose

Placebo = Subject receiving placebo

GMT/C = geometric mean for <anti-RSV A Neutralizing antibody titre, RSV IgG antibody concentration> estimated by the ANOVA model for repeated measures

N = Number of subjects with available results

95% CI = 95% confidence interval (ANOVA model); LL = lower limit, UL = upper limit

PRE= Pre-vaccination at screening

[figure not shown]
PI(D8) = Post-vaccination at Day 8

PI(D31) = Post-vaccination at Day 31

PI(D61) = Post-vaccination at Day 61

PI(D91) = Post-vaccination at Day 91

Template 40 <GMTs, GMCs> and their 95% CIs for <RSV-A neutralising antibody titres, RSV IgG antibody concentration> at each timepoint up to Day <31,91> <PPS for immunogenicity>

RSV MAT 30 = Subject receiving RSVPreF3 low dose

RSV MAT 60 = Subject receiving RSVPreF3 mid dose

RSV MAT 120 = Subject receiving RSVPreF3 high dose

Placebo = Subject receiving placebo

<GMT,C> = geometric mean antibody <titre, concentration> calculated on all subjects

95% CI = 95% confidence interval

PRE = Pre-vaccination at screening

PI(D8) = Post-vaccination at Day 8

[figure not shown]
PI(D31) = Post-vaccination at Day 31

PI(D61) = Post-vaccination at Day 61

PI(D91) = Post-vaccination at Day 91

Note: This graph is provided as an example. For each assay separately, this graph will display the 4 groups and the 5 immuno timepoints: PRE, PI(D8), PI(D31), PI(D61) and PI(D91)

Template 41 Reverse cumulative distribution curves for <anti-RSV-A neutralising antibody titres, RSV IgG antibody concentrations> in each group at pre-vaccination and <Day 8, Day 31, Day 61, Day 91> <PPS for immunogenicity>

[figure not shown]

RSV MAT 30 = Subject receiving RSVPreF3 low dose

RSV MAT 60 = Subject receiving RSVPreF3 mid dose

RSV MAT 120 = Subject receiving RSVPreF3 high dose

Placebo = Subject receiving placebo

Template 42 Kinetics of <GMTs, GMCs> for <anti-RSV A neutralizing antibody titres, RSV IgG antibody concentration> on subjects with results available at all timepoints up to Day 91 <PPS for immunogenicity>

RSV MAT 30 = Subject receiving RSVPreF3 low dose

[figure not shown]
RSV MAT 60 = Subject receiving RSVPreF3 mid dose

RSV MAT 120 = Subject receiving RSVPreF3 high dose

Placebo = Subject receiving placebo

Please note that graph is provided as example (our groups and timepoints are different)

Template 43 Individual results of <anti-RSV neutralizing antibody titres, RSV IgG antibody concentration> at <Day 31,61,91> versus pre-vaccination in <RSV MAT 30, RSV MAT 60, RSV MAT 120> and Placebo <PPS for immunogenicity>

RSV MAT 30 = Subject receiving RSVPreF3 low dose

RSV MAT 60 = Subject receiving RSVPreF3 mid dose

RSV MAT 120 = Subject receiving RSVPreF3 high dose

Placebo = Subject receiving placebo

Figure is only a template. Actual will be done for the assays mentioned in the titles and for each group.

Template 44 Geometric Mean ratios with corresponding 95% confidence interval between anti-RSV F IgG antibody concentrations and anti-RSV-A neutralising antibody titres at pre-vaccination (PPS for immunogenicity)

Timing	Group description	N	IgG Total GMC	GM ratio				Value	95% CI
				95% CI		95% CI			
PRE	<each group>								
PRE									
PRE									
PRE									

<each group>:

RSV MAT 30 = Subject receiving RSVPreF3 low dose

RSV MAT 60 = Subject receiving RSVPreF3 mid dose

RSV MAT 120 = Subject receiving RSVPreF3 high dose

Placebo = Subject receiving placebo

N = Number of subjects with available results at pre-vaccination for IgG antibody concentration and RSV-A neutralizing antibody

GMC = Geometric mean antibody concentration calculated on all subjects for anti-RSV F IgG antibody concentration

GMT = Geometric mean antibody titre calculated on all subjects for RSV-A neutralizing antibody titres

GM Ratio=Geometric mean of individual ratio of IgG antibody concentration to RSV-A neutralizing antibody titre for each group

95% CI = 95% confidence interval; LL = lower limit, UL = upper limit

PRE = Pre-vaccination at screening

Template 45 Geometric Mean ratios of fold increase post/pre) with corresponding 95% confidence interval between anti-RSV F IgG antibody concentrations and anti-RSV-A neutralising antibody titres at <Day 8, Day 31, Day 61, Day 91> adjusted by pre-vaccination ratio <PPS for immunogenicity at Day <8, 31, 61, 91>>

Timepoint	Group	N	IgG Total GMF	95% CI		RSV-A neut GMF	95% CI		GMF Ratio			
				95% CI			Value	LL	UL			
				LL	UL							
PI(D31)	<each group>											
PI(D61)												
PI(D91)												

<each group>:

RSV MAT 30 = Subject receiving RSVPreF3 low dose

RSV MAT 60 = Subject receiving RSVPreF3 mid dose

RSV MAT 120 = Subject receiving RSVPreF3 high dose

Placebo = Subject receiving placebo

N = Number of subjects with available results at the two considered time points for IgG antibody concentration and anti-RSV-A neutralizing antibody titres

GMF = Geometric mean of fold increase post over pre-vaccination

GMF Ratio= Geometric mean of individual ratio of fold increase for each group

95% CI = 95% confidence interval; LL = lower limit, UL = upper limit

PRE = Pre-vaccination at screening

PI(D8) = Post-vaccination at Day 8

PI(D31) = Post-vaccination at Day 31

PI(D61) = Post-vaccination at Day 61

PI(D91) = Post-vaccination at Day 91

Template 46 Exploratory comparisons (<GMT, GMC> ratios) between RSV groups with corresponding 95% confidence interval for <anti-RSV A neutralizing antibody titre, anti-RSV F IgG antibody concentration> at Day 31 – Tukey's adjustment <PPS for immunogenicity at Day 31>

	GMT ratio								Tukey's 95% CI		
	Antibody	Group description	N	Adjusted <GMT, GMC>	Group description	N	Adjusted <GMT, GMC>	Ratio order	Value	LL	UL
<Anti-RSV A Neutralizing Antibody, RSV IgG antibody> PI(D8)	RSV MAT 120				RSV MAT 30			RSV MAT 120/RSV MAT 30			
	RSV MAT 120				RSV MAT 60			RSV MAT 120/ RSV MAT 60			
	RSV MAT 60				RSV MAT 30			RSV MAT 60/RSV MAT 30			

RSV MAT 30 = Subject receiving RSVPreF3 low dose

RSV MAT 60 = Subject receiving RSVPreF3 mid dose

RSV MAT 120 = Subject receiving RSVPreF3 high dose

Adjusted GMT = geometric mean antibody titre adjusted for age_cat, center and baseline titre

N = Number of subjects with both pre- and post-vaccination results available

Tukey's 95% CI = 95% confidence interval for the GMT/GMC ratio (ANCOVA model: adjustment for age_cat, center and baseline titre - pooled variance;Tukey's adjustment), LL = lower limit, UL = upper limit

Age_cat is 1 for subject within age interval of 18-32 years and 2 for 33-45 years

PI(D31) = Post-vaccination at Day 31

Template 47 Exploratory comparisons (<GMT, GMC> ratios) between RSV groups with corresponding 95% confidence interval for <anti-RSV A neutralizing antibody titre, anti-RSV F IgG antibody concentration> at Day 31 <PPS for immunogenicity at Day 31>

	GMT ratio								95% CI	
	Group description	N	Adjusted <GMT, GMC>	Group description	N	Adjusted <GMT, GMC>	Ratio order	Value		
<Anti-RSV A Neutralizing Antibody, RSV IgG antibody> PI(D8)	RSV MAT 120			RSV MAT 30			RSV MAT 120/RSV MAT 30			
	RSV MAT 120			RSV MAT 60			RSV MAT 120/ RSV MAT 60			
	RSV MAT 60			RSV MAT 30			RSV MAT 60/RSV MAT 30			

RSV MAT 30 = Subject receiving RSVPreF3 low dose

RSV MAT 60 = Subject receiving RSVPreF3 mid dose

RSV MAT 120 = Subject receiving RSVPreF3 high dose

Adjusted GMT = geometric mean antibody titre adjusted for age_cat, center and baseline titre

N = Number of subjects with both pre- and post-vaccination results available

95% CI = 95% confidence interval for the GMT/GMC ratio (ANCOVA model: adjustment for age_cat, center and baseline titre - pooled variance), LL = lower limit, UL = upper limit

Age_cat is 1 for subject within age interval of 18-32 years and 2 for 33-45 years

PI(D31) = Post-vaccination at Day 31

Template 48 Exploratory comparisons (Geometric mean ratios) between RSV groups with corresponding 95% confidence interval for area under curve (AUC) up to Day 91 for <anti-RSV A neutralizing antibody titre, anti-RSV F IgG antibody concentration> <PPS for immunogenicity>

	GM ratio								95% CI	
	Group description	N	Adjusted <GM>	Group description	N	Adjusted <GM>	Ratio order	Value		
<Anti-RSV A Neutralizing Antibody, RSV IgG antibody> PI(D8)	RSV MAT 120			RSV MAT 30			RSV MAT 120/RSV MAT 30			
	RSV MAT 120			RSV MAT 60			RSV MAT 120/ RSV MAT 60			
	RSV MAT 60			RSV MAT 30			RSV MAT 60/RSV MAT 30			

RSV MAT 30 = Subject receiving RSVPreF3 low dose

RSV MAT 60 = Subject receiving RSVPreF3 mid dose

RSV MAT 120 = Subject receiving RSVPreF3 high dose

Adjusted GM = geometric mean of area under curve (AUC) adjusted for age_cat, center and baseline titre

N = Number of subjects with both pre- and post-vaccination results available

95% CI = 95% confidence interval for the GMT/GMC ratio (ANCOVA model: adjustment for age_cat, center and baseline titre - pooled variance), LL = lower limit, UL = upper limit

Age_cat is 1 for subject within age interval of 18-32 years and 2 for 33-45 years

Template 49 Exploratory comparisons (<GMT, GMC> ratios) between RSV groups and placebo with corresponding 95% confidence interval for <RSV A neutralizing antibody titre, RSV F IgG antibody concentration> at Day 31 <PPS for immunogenicity at Day 31>

								GMT ratio				
										Adjusted 95% CI	Adjusted p-value	
Antibody	Timepoint	Group description	N	<GMT, GMC>	Group description	N	<GMT, GMC>	Ratio order	Value	LL	UL	
<RSV-A NAb, RSV IgG antibody>	PI(D8)	RSV MAT 120			Placebo			RSV MAT 120/Placebo				
		RSV MAT 60			Placebo			RSV MAT 60/ Placebo				
		RSV MAT 30			Placebo			RSV MAT 30/Placebo				

RSV MAT 30 = Subject receiving RSVPreF3 low dose

RSV MAT 60 = Subject receiving RSVPreF3 mid dose

RSV MAT 120 = Subject receiving RSVPreF3 high dose

Placebo = Subject receiving placebo

Adjusted GMT = geometric mean antibody titre adjusted for age_cat, center and baseline titre

N = Number of subjects with both pre- and post-vaccination results available

95% CI = 95% confidence interval for the GMT/GMC ratio (ANCOVA model: adjustment for age_cat, center and baseline titre - pooled variance), LL = lower limit, UL = upper limit

P-values were adjusted according to Dunnett for multiple comparisons to placebo

Age_cat is 1 for subject within age interval of 18-32 years and 2 for 33-45 years

PI(D31) = Post-vaccination at Day 31

Template 50 Descriptive statistics of <anti-RSV A neutralizing antibody titre, anti-RSV F IgG antibody concentration>at pre-vaccination, Day <8, 31, 61, 91><PPS for immunogenicity>

Visit	Parameters	Each Group		95% CI
		N=	LL	
PRE	N with data			
	Mean			
	SD			
	Q1			
	Median			
	Q3			
PI(D8)	...			
PI(D31)	...			
PI(D61)	...			
PI(D91)	...			

<each group>:

RSV MAT 30 = Subject receiving RSVPreF3 low dose

RSV MAT 60 = Subject receiving RSVPreF3 mid dose

RSV MAT 120 = Subject receiving RSVPreF3 high dose

Placebo = Subject receiving placebo

N = total number of subjects

N with data = number of subjects with available results

Value = value of the considered parameter

SD = standard deviation

Q1 and Q3 = 1st and 3rd quantiles

LL, UL = Exact 95% Lower and Upper confidence limits

PRE = Pre-vaccination at screening

PI(D8) = Post-vaccination at Day 8

PI(D31) = Post-vaccination at Day 31

PI(D61) = Post-vaccination at Day 61

PI(D91) = Post-vaccination at Day 91

Template 51 Descriptive statistics of area under the curve up to Day 91 for <anti-RSV A neutralizing antibody titre, anti-RSV F IgG antibody concentration> 91><PPS for immunogenicity>

Timepoint	Parameters	Each Group	
		N=	95% CI
Up to Day 91	N with data		
	Mean		
	SD		
	Q1		
	Median		
	Q3		

<each group>:

RSV MAT 30 = Subject receiving RSVPreF3 low dose

RSV MAT 60 = Subject receiving RSVPreF3 mid dose

RSV MAT 120 = Subject receiving RSVPreF3 high dose

Placebo = Subject receiving placebo

N = total number of subjects

N with data = number of subjects with documentation of the corresponding data

Value = value of the considered parameter

SD = standard deviation

Q1 and Q3 = 1st and 3rd quantiles

LL, UL = Exact 95% Lower and Upper confidence limits

Template 52 Assessment of trend (linear or quadratic) of dose response for <<anti-RSV A neutralizing antibody titre, anti-RSV F IgG antibody concentration> between three RSV vaccine groups at Day 31 <PPS for immunogenicity at Day 31>

Antibody	Trend Test	N	P value
<Anti-RSV A Neutralizing Antibody, RSV IgG antibody>	Linear		
	Quadratic		

<each group>:

RSV MAT 30 = Subject receiving RSVPreF3 low dose

RSV MAT 60 = Subject receiving RSVPreF3 mid dose

RSV MAT 120 = Subject receiving RSVPreF3 high dose

Analysed using ANCOVA fitting treatment as fixed effect and age_cat, center and baseline titre as covariate

Contrast used for evaluating <linear,quadratic> trend is

Age_cat is 1 for subject within age interval of 18-32 years and 2 for 33-45 years

Template 53 Assessment of trend (linear or quadratic) of dose response using area under curve up to Day 91 for <<anti-RSV A neutralizing antibody titre, anti-RSV F IgG antibody concentration> between three RSV vaccine groups <PPS for immunogenicity>

Antibody	Trend Test	N	P value
<Anti-RSV A Neutralizing Antibody, RSV IgG antibody>	Linear		
	Quadratic		

<each group>:

RSV MAT 30 = Subject receiving RSVPreF3 low dose

RSV MAT 60 = Subject receiving RSVPreF3 mid dose

RSV MAT 120 = Subject receiving RSVPreF3 high dose

Analysed using ANCOVA fitting treatment as fixed effect and age_cat, center and baseline titre as covariate

Age_cat is 1 for subject within age interval of 18-32 years and 2 for 33-45 years

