10.6. Derived and transformed data

The study groups will be defined by treatment actually administered.

For a given subject and a given demographic variable, missing measurements will not be replaced.

Safety

- For a given subject and the analysis of solicited symptoms within 7 days post-vaccination, missing or non-evaluable measurements will not be replaced. Therefore the analysis of the solicited symptoms based on the ES will include only vaccinated subjects for doses with documented safety data (i.e., symptom screen completed).
- For analysis of unsolicited adverse events (including SAEs) categorized by primary Medical Dictionary for Regulatory Activities (MedDRA) term, all vaccinated subjects will be considered. Subjects who did not report the event will be considered as subjects without the event.
- For the analysis of concomitant medications, all vaccinated subjects will be considered and analysis will be performed on the ES. Subjects who did not report the concomitant medication will be considered as subjects without concomitant medication.

Immunogenicity

- For a given subject and given immunogenicity measurements, missing or non-evaluable measurements will not be replaced. Therefore, an analysis will exclude subjects with missing or non-evaluable measurements.
- A seronegative subject is a subject whose antibody titre/concentration is below the cut-off value of the assay. A seropositive subject is a subject whose antibody titre/concentration is greater than or equal to the cut-off value of the assay.
- The Geometric Mean Titres/Concentrations(GMT/GMCs) calculations are performed by taking the anti-log of the mean of the log titre transformations. Antibody titres below the cut-off of the assay will be given an arbitrary value of half the cut-off of the assay for the purpose of GMT/GMC calculation. The cut off values are defined by the laboratory before the analysis and will be described in the Statistical Analysis Plan (SAP).

- In order to compute fold increase of antibody titres/concentrations (ratio) between post-vaccination and pre-vaccination titres/concentrations, antibody titres/concentrations below the assay cut-off will be given an arbitrary value of half the cut-off.
- The handling of data below the assay cut offs for GMT/GMC calculations will be described in the SAP.

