11.2.4. Safety

- For a given subject and the analysis of solicited symptoms within 7 days post-vaccination, missing or non-evaluable measurements will not be replaced. Therefore, the analysis of the solicited symptoms based on the Exposed Set will include only vaccinated subjects with documented safety data (i.e., symptom screen completed). More specifically the following rules will be used:
 - Subjects who documented the absence of a solicited symptom after vaccination will be considered not having that symptom after vaccination.
 - When a specific symptom is marked as having occurred following a specific vaccination (i.e. SDTM CE.CEOCCUR=Y for the specified post-vaccination period for the symptom in question), any missing daily recordings will be given imputed values to allow them to contribute to the 'Any' rows but not to specific grade rows of the symptom summary tables.
 - Dose without symptom sheets documented will be excluded.
- For analysis of unsolicited adverse events, such as serious adverse events or adverse events by primary MedDRA term, and for the analysis of concomitant medications, all vaccinated subjects will be considered. Subjects who did not report the event or the concomitant medication will be considered as subjects without the event or the concomitant medication respectively.

Note that for all tables described in this section, the way the percentage of subjects will be derived will depend on the event analysed (see table below for details). As a result, the N value will differ from one table to another.

Event	N used for deriving % per subject for Vaccination phase
Concomitant vaccination	All subjects with study vaccine administered
Solicited general symptom	All subjects with at least one solicited general symptom documented as either present or absent (i.e., symptom screen completed)
Solicited local symptom	All subjects with at least one solicited local symptom documented as either present or absent (i.e., symptom screen completed)
Unsolicited symptom	All subjects with study vaccine administered
Concomitant medication	All subjects with study vaccine administered

11.2.5. Number of decimals displayed:

The following decimal description from the decision rules will be used for the demography, immunogenicity and safety/reactogenicity.

Display Table	Parameters	Number of decimal digits
Demographic characteristics	Mean, median age	1
Demographic characteristics	SD (age)	1
Immunogenicity	Ratio of GMT/C	2

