General SS = Symptom screens used for the collection of general solicited AEs

Local SS = Symptom screens used for the collection of local solicited AEs

Compliance (%) = (n / N) X 100

Template 16 Incidence and nature of <any, grade 2 and 3, grade 3, related, grade 3 related, > adverse events (unsolicited and solicited) <requiring medical attention> reported during the <7,30>-days (Day 1-<7,30>) post-vaccination period <Exposed Set>

Symptoms	<Each group>			<Each group>					
	95% CI		95% CI		95% CI				
N	n	%	LL	UL	N	n	%	LL	UL
Any symptom									
General symptoms									
Local symptoms									

RSV MAT 30 = Subject receiving RSVPreF3 low dose

RSV MAT 60 = Subject receiving RSVPreF3 mid dose

RSV MAT 120 = Subject receiving RSVPreF3 high dose

Placebo = Subject receiving placebo

N = number of subjects with the administered dose

n/% = number/percentage of subjects presenting at least one type of symptom

95% CI = exact 95% confidence interval, LL = Lower Limit, UL = Upper Limit

Template 17 Incidence of solicited local adverse events reported during the 7-day (Days 1-7) post-vaccination period by maximum grading <Exposed Set>

Symptom	Type	<each group>			
		95 % CI		LL	UL
		N	n	%	
Pain	All				
	Grade 1				
	Grade 2				
	Grade 3				
	Medical advice				
	Onset ≤48h				
Redness (mm)	All				
	>20 - ≤50				
	>50 - ≤100				
	>100				
	Medical advice				
	Onset ≤48h				
Swelling (mm)	All				
	>20 - ≤50				
	>50 - ≤100				
	>100				
	Medical advice				
	Onset ≤48h				

RSV MAT 30 = Subject receiving RSVPreF3 low dose

RSV MAT 60 = Subject receiving RSVPreF3 mid dose

RSV MAT 120 = Subject receiving RSVPreF3 high dose

Placebo = Subject receiving placebo

N = number of subjects with the documented dose

n/% = number/percentage of subjects reporting the type of symptoms as maximum intensity during the follow-up

CI = Exact 95% confidence interval; LL = lower limit, UL = upper limit

The maximum intensity of local injection site redness/swelling was coded as follows:

1: >20 mm to ≤ 50 mm

2: > 50 mm to ≤ 100 mm

3: > 100 mm

Please note – to check for AE term in cDISC during dry run

**Template 18 Number of days with solicited local adverse event during the 7-day
(Days 1-7) post-vaccination period <Exposed Set>**

Symptom	Statistic	<Each group>	
		value	value
Pain	n	XXXX	XXXX
	Mean	XX.X	XX.X
	Minimum	XX.X	XX.X
	Q1	XX.X	XX.X
	Median	XX.X	XX.X
	Q3	XX.X	XX.X
	Maximum	XX.X	XX.X
Redness (mm)	n	XXXX	XXXX
	Mean	XX.X	XX.X
	Minimum	XX.X	XX.X
	Q1	XX.X	XX.X

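### Templates 16 and 30 combine solicited and unsolicited AEs but divide by all dosed women, so a missing symptom screen is read as no solicited event and the any, local and general AE percentages fall if screens are missing

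*SAP*

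**What the plan says.** **Solicited symptoms.** Protocol 10.6 states that "missing or non-evaluable measurements will not be replaced. Therefore the analysis of the solicited symptoms based on the ES will include only vaccinated subjects" who have documented safety data. SAP 11.2.4 repeats this and adds "Dose without symptom sheets documented will be excluded". Templates 17 and 20, which report each solicited local and general symptom, match: "N = number of subjects with the documented dose".

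**Unsolicited AEs.** The opposite rule applies. All vaccinated women count, and "Subjects who did not report the event will be considered as subjects without the event" (Protocol 10.6; SAP 11.2.4 is equivalent).

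**Combined tables.** Template 16 gives any, general and local AEs over 7 and 30 days, with versions by grade, relatedness and medical attention. Its numerator is "n/% = number/percentage of subjects presenting at least one type of symptom" and its denominator "N = number of subjects with the administered dose". Template 30, by MedDRA class and term, uses the same denominator.

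**The denominator rule.** SAP 11.2.4 says N depends on the event analysed and warns: "As a result, the N value will differ from one table to another". Its table has rows for solicited general symptoms, solicited local symptoms, unsolicited symptoms, concomitant medication and concomitant vaccination. There is no row for combined AEs. Protocol 10.8.1 and SAP 6.4.1.1, which plan the combined percentages with exact 95% CIs, name no denominator either. The template footnotes are therefore the only place where this N is set.

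**The concern.** The plan keeps two denominators apart for a good reason. Solicited events are known only if the screen was completed, whereas an unsolicited event that nobody reported is taken not to have occurred. The combined tables apply the second convention to both kinds of event. A woman with no screen and no reported AE stays in N and adds nothing to n, which amounts to imputing no solicited event.

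Occurrence of any AE over 30 days heads the primary endpoint (Protocol 10.1, SAP 4.1), and the any, local and general percentages open the safety analysis. SAP 6.4.2.2 also plans a combined summary for registry posting. The same solicited symptom could then carry one percentage in Template 17 or 20 and a lower one in Template 30. Within the report, any local AE could come out below injection-site pain alone.

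**Working it through.** **Plan's own figures.** The documents give no expected any-AE rate and no expected share of missing screens, so no stated figure bears on the point directly. The precision table can be checked and then used as a yardstick. With 125 per group (Protocol 10.4, Table 19), the Clopper-Pearson upper limit for 0/125 is 2.91% (stated 2.9), and 75/125 gives 50.86 to 68.66% (stated 50.9 to 68.7). At 60% the half-width is (68.66 - 50.86)/2 = 8.9 points.

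**Formula.** Notation:
- m: share of dosed women without a symptom screen
- p: true rate, taken to be the same with and without a screen
- q: share of the women without a screen who are still counted through an unsolicited AE

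All three are assumptions. With all dosed women as N:

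- reported percentage = (1 - m)p + mq
- shortfall = p - [(1 - m)p + mq] = m(p - q)

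The shortfall is zero if m = 0 or q = p.

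**Shortfall in points at p = 60%:**

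| m | q = 0 | q = 30% |
|---|---|---|
| 0% | 0 | 0 |
| 1% | 0.6 | 0.3 |
| 2% | 1.2 | 0.6 |
| 5% | 3.0 | 1.5 |
| 10% | 6.0 | 3.0 |

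For p from 30% to 80% with q = 0, the range is 1.5 to 4.0 points at m = 5% and 3.0 to 8.0 points at m = 10%.

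**Coherence between tables.** Suppose 125 women are dosed, 119 have screens, 71 report pain, and no other local event occurs (all assumed).

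- Template 17, pain: 71/119 = 59.7% (exact 95% CI 50.3 to 68.6)
- Template 16, any local: 71/125 = 56.8% (47.6 to 65.6)

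The total is 2.9 points below one of its own components.

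**Comparison with placebo.** Take a true 60% in both groups, q = 0, and 2% missing in one group against 8% in the other. The reported rates are 0.98 x 60 = 58.8% and 0.92 x 60 = 55.2%, a spurious gap of 3.6 points. It favours the vaccine if the 8% is on vaccine and counts against it if the 8% is on placebo. With equal m in both groups and q = 0, both rates shrink by the factor (1 - m) and their ratio does not change.

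**The case against.** There is a serious case on the other side.

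- **The plan may intend all vaccinated women.** The Exposed Set definition (Protocol 10.5.1, SAP 5.1.1) puts every vaccinated woman in a safety analysis, and the primary endpoint is worded for all subjects in all groups. The exclusion rules are written for solicited symptoms and do not expressly govern a composite. This stands to the extent that the text has no explicit rule for composites. It does not make the result coherent: the solicited part of the composite is still handled in a way the plan rejects when it analyses those symptoms alone.
- **The footnotes are provisional.** SAP Annex 3 describes the mock displays as illustrative and adaptable. That makes correction easy but supplies no other rule.
- **Events are captured without a diary.** Unsolicited AEs are also collected by questioning at visits (Protocol Table 15), and unreturned diaries are chased (Protocol 5.6.17). A reader might infer that every woman without diary data is counted as event-free. That is too broad: only those with neither a screen nor a reported AE are, which is why q enters the formula. It helps less in the local row, because the expected injection-site reactions (pain, redness, swelling) are themselves the solicited terms.
- **Readers can see screen return.** Template 15 reports compliance by group, so the effect can be bounded. It is not corrected.
- **The size is modest.** At p = 60% and 5% missing, the shortfall is at most 3 points against a CI half-width of about 9. That is true, but a systematic shift is not absorbed by an interval that describes sampling error.

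**Conclusion.** The combined tables use a denominator that is inconsistent with the plan's handling of solicited data, and their percentages are biased downward whenever screens are missing. At an assumed 60% rate the shortfall is 1.5 to 3 points at 5% missing (q from 30% to 0), 3 to 6 points at 10%, and nothing at 0%. The actual share of missing screens is not in the documents.

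Three stronger conclusions might be drawn, and the documents do not support them:

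- That the any-AE percentages are understated outright. The effect depends on missing screens and disappears if all are returned.
- That the bias always makes the vaccine look safer. Absolute rates can only be lowered, but the same denominator applies to placebo, so the contrast can move either way.
- That the primary endpoint as a whole is affected. The per-symptom results in Templates 17 and 20 already use documented women, and the unsolicited-only and SAE tables follow their own stated rule.

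The point merits a correction before the Day 91 analysis, when the study statistician is unblinded. It does not call the design into question.

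**What to change.** 1. Add a row for combined solicited and unsolicited AEs to the denominator table in SAP 11.2.4.
2. Amend the footnotes of Templates 16 and 30 so that N is the women with the relevant screen documented: the local screen for the local row, the general screen for the general row, and at least one screen for the any row. Template 30 has a single N per group in its heading, so its footnote should say which N applies to the coded solicited terms.
3. Do not add women without screens to N only because they reported an event. They would then enter only as cases, which biases upward. At p = 60% and q = 30% the result is (0.95 x 0.60 + 0.05 x 0.30)/(0.95 + 0.05 x 0.30) = 0.585/0.965 = 60.6% at m = 5%, and 0.57/0.93 = 61.3% at m = 10%.
4. Show the all-vaccinated percentage, with all known events, alongside as a sensitivity result. The documented-only figure assumes that screen return is unrelated to symptoms, and the pair shows how much depends on the choice.
5. Keep all dosed women as N for the unsolicited-only and SAE tables.

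The cost is one table row, two footnotes and one extra percentage. N will differ slightly between tables, which SAP 11.2.4 already accepts. AEs in women without screens will appear only in the sensitivity figures and the tables that keep all dosed women.
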